4.2. Phase 2 Analysis: Condition-level Comparisons of Change in Beliefs

Model 1: Change in Beliefs from Session 1 to Session 2

For the Phase 2 analysis, we will conduct treatment vs. control comparisons of change in beliefs about the negative health consequences of smoking contained in the warnings. Note that participants in the control condition will be exposed to a random selection of one of four Surgeon General’s (SG) warnings; thus, each analysis will compare the change in belief scores between a particular treatment condition and the control group as averaged across the four SG warnings (i.e., we will compare treatment scores to a single control group score, rather than conducting separate analyses for each SG warning within the control condition).

For each experimental condition, the survey includes an item or series of items in which respondents are asked to rate their level of agreement with a statement about a negative health consequence corresponding to the warning for that condition. The number of items associated with a particular warning ranges from 1 to 4. These items are assessed once during Session 1 before stimuli exposure, and then again following second stimuli exposure in Session 2. Table 5 provides a summary of the comparisons, dependent variables, and analysis approach for each of the Phase 2 analyses.

Table 5. Phase 2 Analyses

Analysis #	Comparison	Dependent Variable(s) [All 5-level “Strongly disagree” to “Strongly agree” response options]	Analysis
-------------------	-------------------	---	-----------------

1	Condition 1 vs. Control (0)	A1_1. Cigarettes are addictive	Ordinal logistic regression
2	Condition 2 vs. Control (0)	A2_1. Tobacco smoke can harm your children	Ordinal logistic regression
3	Condition 3 vs. Control (0)	A3_1. Smoking can kill you	Ordinal logistic regression
4	Condition 4 vs. Control (0)	A4_1. Smoking causes fatal lung disease in nonsmokers	Ordinal logistic regression
5	Condition 5 vs. Control (0)	A5_1. Quitting smoking now greatly reduces serious risks to your health	Ordinal logistic regression
6	Condition 6 vs. Control (0)	A6_1. Smoking causes head cancer A6_2. Smoking causes neck cancer	Linear regression (if scaled); ordinal logistic regression (if items treated separately)
7	Condition 7 vs. Control (0)	A7_1. Smoking causes bladder cancer, which can lead to bloody urine A7_2. Smoking causes bladder cancer	Linear regression (if scaled); ordinal logistic regression (if items treated separately)

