8	Condition 8 vs. Control (0)	A8_1. Smoking during pregnancy stunts fetal growth	Ordinal logistic regression
9	Condition 9 vs. Control (0)	A9_1. Smoking causes heart disease A9_2. Smoking causes strokes A9_3. Smoking clogs arteries A9_4. Smoking clogs arteries, which causes heart disease A9_5. Smoking clogs arteries, which causes strokes	Linear regression (if scaled); ordinal logistic regression (if items treated separately)
10	Condition 10 vs. Control (0)	A10_1. Smoking causes COPD, a lung disease that can be fatal A10_2. Smoking causes COPD A10_3. Smoking causes a lung disease that can be fatal	Linear regression (if scaled); ordinal logistic regression (if items treated separately)
11	Condition 11 vs. Control (0)	A10_1. Smoking causes COPD, a lung disease that can be fatal A10_2. Smoking causes COPD	Linear regression (if scaled); ordinal logistic regression

		A10_3. Smoking causes a lung disease that can be fatal	regression (if items treated separately)
12	Condition 12 vs. Control (0)	A12_1. Smoking reduces blood flow, which can cause erectile dysfunction A12_2. Smoking reduces blood flow A12_3. Smoking can cause erectile dysfunction	Linear regression (if scaled); ordinal logistic regression (if items treated separately)
13	Condition 13 vs. Control (0)	A13_1. Smoking reduces blood flow to the limbs, which can require amputation A13_2. Smoking reduces blood flow to the limbs A13_3. Smoking can lead to amputation	Linear regression (if scaled); ordinal logistic regression (if items treated separately)
14	Condition 14 vs. Control (0)	A14_1. Smoking causes type 2 diabetes, which raises blood sugar. A14_3. Smoking can cause Type 2 Diabetes	Linear regression (if scaled); ordinal logistic regression (if items treated separately)
15	Condition 15 vs. Control (0)	A15_1. Smoking causes age-related macular degeneration, which can lead to blindness A15_2. Smoking causes age-related macular degeneration A15_3. Smoking can lead to blindness	Linear regression (if scaled); ordinal logistic regression (if items treated separately)
16	Condition 16 vs. Control (0)	A16_1. Smoking causes cataracts, which can lead to blindness A16_2. Smoking causes cataracts	Linear regression (if scaled); ordinal logistic regression (if items treated separately)

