The items being used to measure beliefs have Likert-type response scales. Conceptually, the response categories for a Likert response scale represent an underlying belief continuum. For warning statements with multiple corresponding items, we will assess whether to scale the items, using the following protocol:

- 1) Run a test of internal consistency reliability using Cronbach's alpha (Cronbach, 1951) on all of the items in a domain. If the test indicates "modest" reliability of $\alpha \geq 0.70$ (Nunnally & Bernstein, 1994), scale the items.

- 2) If $\alpha < 0.70$, but all item-total correlations (i.e. the correlation between the item score and the overall scale score) are ≥ 0.4 , scale the items (Item-total correlations of between 0.30—0.40 and greater have been suggested as sufficiently discriminating (Nunnally & Bernstein, 1994; Traub, 1994; Leong & Austin, eds., 2006)
- 3) If criteria 1 and 2 are not met, determine whether the scale alpha would increase to ≥ 0.70 if any items were deleted from the scale (i.e. using Stata’s “alpha” command with “item” option specified). If the alpha value threshold would be met by dropping an item or items:
 - a. Drop those items to form a scale with $\alpha \geq 0.70$
 - b. Also run analyses of each item individually
- 4) Otherwise, run analyses of each item individually

We are measuring beliefs at each study session. The above procedure to inform the scaling of the belief items will be made on the beliefs assessed at Session 1 (baseline) and then applied to the beliefs measured at the remaining sessions. We do not expect the measurement structure of beliefs to change over a longitudinal sample over a relatively short period of time. Assuming attrition across study sessions, basing the measurement structure on the Session 1 sample utilizes the largest available sample.

To determine the GHW’s immediate impact on targeted beliefs, we will examine the extent to which pre-post differences in beliefs vary between those exposed to GHW (treatment) and SG warnings (control). The general form of this analysis approach is as follows:

$$(\text{Belief}^T_{S2} - \text{Belief}^T_{S1}) - (\text{Belief}^C_{S2} - \text{Belief}^C_{S1})$$

where Belief represents the average value (for continuous variables) or probability of being in a higher response category (for ordinally-treated variables), among those in a Treatment (*T*) or Control (*C*) group, at Session 2 (*S2*) or Session 1 (*S1*).

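### In six Phase 2 item sets, joined statements are scaled with their own parts: overlap inflates alpha, step 2 merges what alpha does not, and no item-level result is required afterwards

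*SAP*

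**What the plan says.** SAP section 4.2 sets a four-step protocol, applied to the Session 1 data, for warnings with more than one belief item.

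- **Step 1** computes Cronbach's "alpha (Cronbach, 1951) on all of the items in a domain" and scales them if alpha is at least 0.70.
- **Step 2** scales a set with lower alpha if every item-total correlation is at least 0.4. It defines that correlation as "the correlation between the item score and the overall scale score", so the item is part of its own total.
- **Step 3** drops items if that brings alpha to 0.70. Step 3b then adds: "Also run analyses of each item individually".
- **Step 4** analyses items one by one if nothing else applies.

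Item-level models are therefore required only at steps 3b and 4. A set scaled at step 1 or 2 gives one linear regression. The section counts 16 Phase 2 tests, one per warning.

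Table 5 lists the items. Analysis 12 has "A12_1. Smoking reduces blood flow, which can cause erectile dysfunction A12_2. Smoking reduces blood flow A12_3. Smoking can cause erectile dysfunction". Analyses 10 and 11 share "A10_1. Smoking causes COPD, a lung disease that can be fatal A10_2. Smoking causes COPD A10_3. Smoking causes a lung disease that can be fatal". Analyses 13 and 15 have the same form: the full warning sentence and both of its clauses. Analysis 9 does not hold the full warning sentence. It holds three single statements (heart disease, strokes, clogged arteries) and two compounds of them: "A9_4. Smoking clogs arteries, which causes heart disease A9_5. Smoking clogs arteries, which causes strokes".

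**The concern.** Alpha is used here to decide whether several items express one belief. It depends on the average inter-item correlation and the number of items. An item that restates two others will tend to correlate with both, whether or not those two correlate with each other. Including it raises alpha for a reason unrelated to whether the distinct beliefs belong together.

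In analysis 12, for example, the result may be an average over reduced blood flow, erectile dysfunction and the sentence that joins them. If a warning shifts only the less familiar consequence, the average dilutes the shift. If the average moves, the planned output does not show which consequence moved, although section 4.2 describes its aim as the effect on the beliefs each warning targets. This touches 6 of the 16 Phase 2 comparisons, and the parallel Session 3 analyses (Model 2).

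**Working it through.** **Inputs.** From the SAP: the item sets (Table 5); the thresholds 0.70 and 0.4 (section 4.2); 2,080 control and 480 per treatment at Session 1 with 50% retention, hence 1,040 and 240 at Session 2 (section 3); a difference of 0.3 with SD 1, two-sided (section 3, where it is set on a 7-point scale, while the belief items have 5 levels). Assumed: all inter-item correlations, and equal item variances. The SAP states no expected alpha, so there is no figure of its own to reproduce.

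**1. Alpha with and without the joined item.** alpha = k·r̄ / (1 + (k − 1)·r̄), where r̄ is the mean inter-item correlation.

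- Two items reach 0.70 at r = 0.538. Three items reach it at r̄ = 0.4375.
- With part-part correlation p and sentence-part correlation c, r̄ = (p + 2c)/3, so the set passes when c ≥ (1.3125 − p)/2. That is c ≥ 0.656, 0.606, 0.556 and 0.506 for p = 0, 0.1, 0.2 and 0.3.
- Example: p = 0.20, c = 0.60 gives r̄ = 1.40/3 = 0.467 and alpha = 1.40/1.933 = 0.72. The two parts alone give 0.40/1.20 = 0.33.
- Counter-example: p = 0.10 gives 0.635 at c = 0.50 and 0.696 at c = 0.60. Both fail step 1.
- Analysis 9, with components at 0.10, each compound at 0.60 with its own parts and 0.30 with the other disease, and the two compounds at 0.60: the ten correlations sum to 3 × 0.10 + 4 × 0.60 + 2 × 0.30 + 0.60 = 3.90, so r̄ = 0.39 and alpha = 1.95/2.56 = 0.76. The three components alone give 0.30/1.20 = 0.25.

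**2. How often overlap carries a set past 0.70.** Simulated 5-level three-item sets, with symmetric or skewed cut-points and the sentence modelled as the average or the minimum of its clauses, gave these ranges of alpha:

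| Latent clause correlation | Reliability 1.0 | 0.9 | 0.8 | 0.7 |
|---|---|---|---|---|
| 0 to 0.1 | 0.628–0.738 | 0.599–0.698 | 0.557–0.653 | 0.511–0.605 |
| 0.2 | 0.730–0.774 | 0.699–0.734 | 0.656–0.690 | 0.605–0.641 |
| 0.3 | 0.771–0.807 | 0.742–0.769 | 0.693–0.723 | 0.639–0.675 |

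At latent correlation 0.2 and reliability 0.9, the clauses alone gave 0.26 to 0.28.

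**3. What step 2 does with the sets that fail.** For k items with common correlation r, the uncorrected item-total correlation is √((1 + (k − 1)r)/k). At r = 0 this is 1/√3 = 0.577 for three items and 1/√2 = 0.707 for two. Both exceed 0.4. For two items it stays at or above 0.4 down to r = −0.68. In every simulated set above, the lowest value was 0.65 or more.

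**4. Whether repairing step 2 alone is enough.** At p = 0.20, c = 0.60 the set passes step 1 and never reaches step 2. Even if it did, the lowest corrected item-rest correlation, that of a clause with the sum of the other two items, is (0.60 + 0.20)/√(2 + 2 × 0.60) = 0.80/1.789 = 0.447, which also passes 0.4.

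**5. Dilution.** SE = SD·√(2(1 − ρ)(1/240 + 1/1040)), where ρ is the within-person correlation, taken as equal for item and scale. For p = 0.20, c = 0.60 the three-item mean has SD √((3 + 2 × 1.40)/9) = 0.803. Let one clause move 0.3. The mean moves 0.2 if the sentence item also moves 0.3, and 0.1 if the sentence item does not move. Unadjusted power:

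| ρ | Moving item alone | Scale, clause and sentence move | Scale, clause only moves | Scale, all three move |
|---|---|---|---|---|
| 0 | 0.84 | 0.69 | 0.23 | 0.96 |
| 0.2 | 0.91 | 0.79 | 0.28 | 0.99 |
| 0.4 | 0.97 | 0.89 | 0.36 | 1.00 |
| 0.6 | 1.00 | 0.97 | 0.49 | 1.00 |
| 0.8 | 1.00 | 1.00 | 0.79 | 1.00 |

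**The case against.** **Step 1 is not the deciding gate.** As the SAP stands, a set that fails alpha is merged by step 2 anyway, so shared wording changes little in practice, and a change to step 1 alone would have no effect. This stands. The overlap remains a separate fault, because a repaired step 2 would still let overlapping sets through (item 4 of the working).

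**Alpha may not pass.** A reader might infer that overlap necessarily takes nearly unrelated beliefs past 0.70. The SAP does not support that. It gives no inter-item correlations, and in the simulations such clauses stayed below 0.70 once the items carried any error. The supportable statement is that weakly related beliefs can pass.

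**The parts may be well correlated.** All items are agreement ratings of smoking harms by the same respondents, and A10_2 and A10_3 describe one disease. If two parts correlate at 0.54 or more, they scale on their own and the overlap is irrelevant. This is a fair point that only the data can settle. The wording overlap is also close rather than literal in places: A13_1 and A13_3 use different verbs for amputation.

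**The power loss depends on the scenario.** When the sentence moves with its clause, the loss largely vanishes at within-person correlations of 0.6 or more, and Table 3 of the SAP extends to 0.8. When all items move, scaling gains power (0.96 against 0.84 at ρ = 0). The comparator is also a single item already known to move, without multiplicity adjustment. All this stands. The loss persists at high correlations only if the sentence item does not move at all.

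**The plan promises no clause-level attribution.** Section 4.2 allows the belief to be measured by a set of statements and plans one test per warning. That argues for keeping the scale as the tested outcome, not for leaving the item results unreported.

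**Not every multi-item set is affected.** Analysis 6 has two parallel items. Analyses 7, 14 and 16 pair the sentence with one clause, so no two separate clauses are merged.

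**Conclusion.** The point holds as a weakness of steps 1 and 2 taken together, for analyses 9, 10, 11, 12, 13 and 15. Three parts of it rest on the SAP text and algebra alone: joined statements sit in the same alpha as their parts; step 2 accepts even uncorrelated items (0.577 for three, 0.707 for two); and a set scaled at either step needs no item-level analysis.

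The size of the alpha inflation rests on assumed correlations. It is 0.72 against 0.33 in the three-item example and 0.76 against 0.25 in the analysis 9 example, and lower sentence-part correlations leave alpha under 0.70. The dilution figures further assume item SD 1, 50% retention and the stated pattern of movement. They show a possible loss, not an expected one. The firmer consequence is interpretive: a significant or null scale result cannot be traced to a particular health belief. This should be changed before analysis, but it does not invalidate the Phase 2 comparisons.

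**What to change.** 1. **Report the items whenever a set is scaled.** Extend step 3b to sets scaled at steps 1 and 2: give each item's difference-in-difference beside the scale result, labelled descriptive and kept outside the Benjamini-Hochberg family. This works whichever step merged the items.
2. **Judge scalability on non-overlapping items.** Use A9_1 to A9_3; A10_2 and A10_3; A12_2 and A12_3; A13_2 and A13_3; A15_2 and A15_3. In the same change, replace the item-total correlation in step 2 by the corrected item-rest correlation. Without that correction the two-item sets would still pass step 2 at any correlation above about −0.68.
3. **State what happens to the joined item** when its parts pass: whether it rejoins the scale or is analysed separately.

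The cost is SAP wording and a few more model runs on data already planned. The downside is that some sets may no longer scale, which would add item-level tests to the Phase 2 family beyond the 16 now counted.

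### Step 2 of the belief-scaling rule correlates each item with a total that contains it, so for two- and three-item sets of similar SD the 0.4 cut-off screens out almost nothing

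*SAP*

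**What the plan says.** Section 4.2 of the SAP sets a four-step rule for warnings with several belief items. Step 1 scales the items if alpha is at least 0.70. Step 2 applies when alpha is lower: if all item-total correlations "are ≥ 0.4 , scale the items". The SAP defines the item-total correlation as "the correlation between the item score and the overall scale score" and nowhere removes the item from that score. Step 3 opens with "If criteria 1 and 2 are not met" and tells the analyst to "determine whether the scale alpha would increase to ≥ 0.70 if any items were deleted from the scale"; if so, those items are dropped and each item is also analysed singly. Step 4 is the fallback: "Otherwise, run analyses of each item individually".

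The rule is applied to Session 1 data and carried forward. It determines whether a comparison uses one linear model on a scale or ordinal logistic models item by item.

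Table 5 has ten multi-item comparisons. Conditions 6, 7, 14 and 16 have two items, for example "A6_1. Smoking causes head cancer A6_2. Smoking causes neck cancer". Conditions 10, 11, 12, 13 and 15 have three, for example "A12_1. Smoking reduces blood flow, which can cause erectile dysfunction A12_2. Smoking reduces blood flow A12_3. Smoking can cause erectile dysfunction". Condition 9 has five. (The text says "The number of items associated with a particular warning ranges from 1 to 4", which does not match the five items listed for Condition 9.)

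**The concern.** Step 2 is meant to show that the items hang together despite a low alpha. A total that includes the item gives a positive correlation even when the items have nothing in common, because part of the total is the item itself. With few items that part is large. If the built-in value already exceeds 0.4, step 2 accepts sets that steps 3 and 4 were written to catch. Items that do not measure one belief would then be averaged into a single outcome, and a change in one of them would be harder to detect.

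**Working it through.** **Inputs.** From SAP section 4.2: the definition of the item-total correlation, the cut-offs 0.4 and 0.70, and the order of the steps. From Table 5: set sizes k = 2, 3 and 5. The SAP gives no inter-item correlations or item SDs and no computed figure for this rule, so there is nothing to reproduce. Equal SDs and a common correlation r are assumed at first, then relaxed.

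**Formulas.**
- Item-total, item included: √[(1 + (k−1)r)/k]
- Alpha: kr/[1 + (k−1)r]
- Item-rest, item excluded: (k−1)r/√[(k−1)(1 + (k−2)r)]

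**Mutually unrelated items (r = 0, alpha = 0).** The item-total correlation is 1/√k.

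| k | item-total at r = 0 | r below which step 2 fails | r needed for alpha 0.70 |
|---|---|---|---|
| 2 | 0.71 | −0.68 | 0.54 |
| 3 | 0.58 | −0.26 | 0.44 |
| 5 | 0.45 | −0.05 | 0.32 |

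The third column solves (1 + (k−1)r)/k = 0.16. A simulation of 9,760 respondents with independent, skewed five-level items agrees: item-total 0.70 to 0.71 (k = 2), 0.57 to 0.59 (k = 3) and 0.435 to 0.455 (k = 5), with alpha between −0.001 and 0.031.

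**One unrelated item among related ones, equal SDs.** If the other k−1 items correlate at r, the total has variance k + (k−1)(k−2)r and the odd item's item-total correlation is 1/√[k + (k−1)(k−2)r].
- k = 3: 1/√(3 + 2r), which is at least 1/√5 = 0.447 even at r = 1. The odd item always passes.
- k = 5: 1/√(5 + 12r), below 0.4 once 5 + 12r > 6.25, that is r > 0.104. Alpha is (5/4)·12r/(5 + 12r), which stays below 0.70 until r is about 0.53. Between these values step 2 fails and step 3 is reached.

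**Example where step 3 is bypassed.** Three items, two correlating at 0.6 and one unrelated to both. The variance of the total is 3 + 1.2 = 4.2. Alpha is 1.5 × (1 − 3/4.2) = 0.43. The item-total correlations are 1/√4.2 = 0.49 for the odd item and 1.6/√4.2 = 0.78 for the other two, so step 2 scales all three. Step 3 would have dropped the odd item, leaving alpha 1.2/1.6 = 0.75.

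**Unequal SDs, r = 0.** With one item of SD s and the others of SD 1, step 2 fails when s < √[0.16(k−1)/0.84]: 0.44 (k = 2), 0.62 (k = 3), 0.87 (k = 5).

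**Effect on the outcome.** Suppose one of three unrelated unit-SD items moves by 0.3 and the others do not. The mean moves by 0.3/3 = 0.10, on a score with SD 1/√3 = 0.577. The standardised effect is 0.10/0.577 = 0.17, against 0.30 for the item alone.

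**The case against.** Several points against the concern stand.

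- Step 2 operates only when alpha is below 0.70. Many Table 5 items restate a warning and its parts, so step 1 may settle most sets. Correlations near zero are assumed, not documented.
- A reader might infer that steps 3 and 4 can be reached only with negative correlations or very unequal SDs. That is untrue for Condition 9: a single unrelated item is caught once the other four correlate above about 0.10, and at r = 0 an SD ratio of 0.87 is enough.
- A reader might also infer that the flaw decides the outcome in all ten multi-item comparisons. The four-step rule as a whole does that; step 2 decides only the sets that fail step 1. Conditions 10 and 11 also share one item set.
- It is tempting to say that the effect shrinks to a third (0.1 against 0.3). That ignores the smaller SD of the average. Dilution can also occur in scales with a high alpha, and the randomised comparison of a mean score remains valid.
- An alpha of 0.70 is not an absolute requirement in this plan, because step 2 is a deliberate alternative to it.

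None of this rescues step 2 for two or three items. An alternative criterion should still tell related items from unrelated ones, and a cut-off that unrelated items exceed by construction does not.

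**Conclusion.** The point holds in a limited form. As written, step 2 has almost no screening power for the two- and three-item sets, which make up 9 of the 10 multi-item comparisons, provided item SDs are similar. For those sets it pre-empts steps 3 and 4 when alpha is below 0.70, unless items are clearly negatively correlated. For Condition 9 the rule keeps some force: five mutually unrelated items of near-equal SD pass, but one odd item among related ones usually does not. If the set had four items, as the text implies, mutually unrelated items would score 1/√4 = 0.50 and also pass.

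How often any of this will matter cannot be judged from the SAP. Where it does, the cost is loss of sensitivity and a composite that is hard to interpret. Nothing here shows an inflated Type I error.

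**What to change.** In step 2, define the correlation as the corrected item-rest correlation, that is, the item against the sum of the other items in the set, and keep the 0.4 cut-off. For two items this is simply the inter-item correlation. Unrelated items then score 0 and fail. For equal-variance, equally correlated items, the smallest r that passes becomes 0.40 (k = 2), 0.33 (k = 3) and 0.27 (k = 5), and the lowest alpha admitted about 0.57, 0.59 and 0.65. The change does not impose alpha of 0.70, nor is it meant to.

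The edit is a few words, but it has one consequence. Some sets may go to item-by-item analysis, which takes Phase 2 above its stated 16 tests. If every set were split, the count would be 6 + 4×2 + 5×3 + 5 = 34. Steps 3 and 4 already allow this, so the SAP should say how item-level tests enter the FDR family and update its size. The number of items for Condition 9 should be reconciled at the same time.
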